6.2.3 Unsolicited Adverse Events

All AEs spontaneously reported by the subject and/or in response to an open question from study staff or revealed by observation, physical examination or other diagnostic procedures must be recorded on the appropriate e-CRF.

Unsolicited AEs of all severities will be reported from the time of study device administration through study termination.

6.2.4 Adverse Event Reporting

Information on all AEs should be recorded on the appropriate e-CRF. All clearly related signs, symptoms and results of diagnostic procedures performed because of an AE should be grouped together and recorded as a single diagnosis. If the AE is a clinical laboratory abnormality that is part of a clinical condition or syndrome, it should be recorded as the syndrome or diagnosis and be described in terms of duration (start and stop date).

6.2.5 Definition of a Serious Adverse Event (SAE)

An SAE is defined in 21 CFR 312.32 as follows: “An AE is considered serious if, in the view of either the participating clinical site PI or appropriate sub-investigator or the sponsor, it results in any of the following outcomes:

- Death,
- A life-threatening AE,

- Inpatient hospitalization or prolongation of existing hospitalization,
- A persistent or significant incapacity or substantial disruption of the ability to conduct normal life functions,
- Or a congenital anomaly/birth defect.

Important medical events that may not result in death, are not immediately life-threatening, or require hospitalization may be considered serious when, based upon appropriate medical judgment, they may jeopardize the patient or subject and may require medical or surgical intervention to prevent one of the outcomes listed in this definition. An example of such a medical event would be an allergic bronchospasm requiring intensive treatment in an emergency room or at home to prevent the development of one of the definitions above.

“Life-threatening” refers to an AE that at occurrence represents an immediate risk of death to a subject. An event that may cause death if it occurs in a more severe form is not considered life-threatening. Similarly, a hospital admission for an elective procedure is not considered an SAE.

All SAEs, as with any AE, will be assessed for severity and relationship to study intervention. All SAEs will be recorded on the appropriate SAE e-CRF.

All SAEs will be followed through resolution or stabilization by a study clinician, licensed to make medical diagnoses and listed as the participating clinical site PI or appropriate sub-investigator.

All SAEs will be reviewed and evaluated by the Sponsor and will be reported to the IRB. This report will include severity, association with the study device, action(s) taken, and outcome.

6.2.6 Serious Adverse Event Reporting

Any AE that meets a protocol-defined criterion as an SAE must be submitted immediately (within 24 hours of site awareness) on an SAE form to EmitBio Inc. Pharmacovigilance:

EmitBio™ Pharmacovigilance

SAE Hot Line: [name] or [name]

Text Immediate Report: [name]

SAE Email: [contact]

In addition to the SAE form, all SAE data must be entered into the SAE e-CRF.

Other supporting documentation of the event may be requested by EmitBio™ Pharmacovigilance and should be provided as soon as possible. The Sponsor Medical Monitor will review and assess the SAE for regulatory reporting and potential impact on study subject safety and protocol conduct.

At any time after completion of the study, if the participating clinical site PI or appropriate sub-investigator becomes aware of an SAE that is suspected to be related to study product, the participating clinical site PI or appropriate sub-investigator will report the event to the EmitBio™ Pharmacovigilance Group.

Regulatory Reporting of Device-related SAEs

Following notification from the participating clinical site PI or appropriate sub-investigator, EmitBio Inc., as the sponsor, will report to the FDA and will copy the clinical site investigators on all reports of potential serious risks from clinical studies of RD19, as soon as possible. EmitBio Inc. will report to the FDA any unexpected fatal or life-threatening suspected adverse reaction as soon as possible, but in no case later than 7 calendar days after the sponsor's initial receipt of the information. If the event is not fatal or life-threatening, an SAE safety report will be submitted within 15 calendar days after the sponsor determines that the information qualifies for reporting as specified in 21 CFR Part 312.32.

Relevant follow-up information to the safety report will be submitted as soon as the information is available. Upon request from FDA, EmitBio™ will submit to the FDA any additional data or information that the agency deems necessary, as soon as possible, but in no case later than 15 calendar days after receiving the request.

SAEs that are not considered related to RD19 will not be reported to the FDA.

6.2.7 Classification of an Adverse Event

The determination of seriousness, severity and causality will be made by an on-site investigator who is qualified (licensed) to diagnose AE information, provide a medical evaluation of AEs and classify AEs based upon medical judgment. This includes, but is not limited to, physicians, physician assistants and nurse practitioners.

6.2.8 Severity of Adverse Events

All AEs or SAEs will be assessed for severity, according to the toxicity grading scales provided at **Appendix 2**.

For AEs not included in the protocol-defined grading system, the following guidelines will be used to describe severity.

- **Mild (Grade 1)**: Events that are usually transient and may require only minimal or no treatment or therapeutic intervention and generally do not interfere with the subject's usual activities of daily living.
- **Moderate (Grade 2)**: Events that are usually alleviated with additional specific therapeutic intervention. The event interferes with usual activities of daily living, causing discomfort but poses no significant or permanent risk of harm to the research subject.
- **Severe (Grade 3)**: Events interrupt usual activities of daily living, or significantly affects clinical status, or may require intensive therapeutic intervention. Severe events are usually incapacitating.

AEs characterized as intermittent require documentation of onset and duration of each episode. The start and stop date of each reported AE will be recorded on the appropriate e-CRF. Changes in the severity of an AE will be documented to allow an assessment of the duration of the event at each level of intensity.

6.2.9 Relationship to Study Intervention

For each reported adverse event, the participating clinical site PI or qualified designee must assess the relationship of the event to the study device using the following guidelines:

- Related – The AE is known to occur with the study intervention, there is a reasonable possibility that the study intervention caused the AE, or there is a close temporal relationship between the study intervention and event. Reasonable possibility means that there is evidence to suggest a causal relationship between the study intervention and the AE.
- Null Determination – The direction and magnitude towards related and not related is null. The investigator is stating simply, “I cannot determine a relationship”.
- Not Related – There is not a reasonable possibility that the administration of the study intervention caused the event, there is no temporal relationship between the study intervention and event onset, or an alternate etiology has been established.

6.2.10 Time Period and Frequency for Event Assessment and Follow-Up

For this study:

- Solicited and Unsolicited AEs will be recorded by volunteers daily on the Diary Card and collected on Clinic visit days 7, 14 and any unscheduled clinical trial unit visits.

6.2.11 Adverse Event Reporting to Study Subjects

- All device-attributed AEs and SAEs will be reported to participants in the study to better inform them of the potential risks vs. benefits of participation.

6.2.12 Pregnancy Reporting

- All positive urine pregnancy tests will be reported during screening and at the end of the study. Women who screen positive for pregnancy will be encouraged to see their primary health care provider for a serological confirmatory test.

7. STATISTICAL CONSIDERATIONS

7.1 Statistical Hypotheses

This is a phase I, open-label, safety study and is not designed to test any statistical hypotheses. Rather, this is a descriptive study intended to obtain preliminary estimates in healthy adults of the safety, including reactogenicity, of the EmitBio™ RD19 Device.

7.2 Sample Size Determination

SAMPLE SIZE CONSIDERATION - OPEN LABEL

This study is designed as an open-label study, without a placebo arm. Given the small sample size, the use of a placebo group is unlikely to improve understanding of AEs. Additionally, having the study unblinded will facilitate the need for rapid review and dissemination of study data for public health reasons.

Rare AEs are not demonstrable in a clinical study of this size; however, the probabilities of observing one or more AEs given various true event rates are presented in the table below. With the assumption that all enrolled subjects will likely complete the trial and safety visits in this relatively short duration study, the following statistical considerations apply. With 25 subjects, the chance of observing at least one AE of probability 20% or more is approximately 97%. Therefore, if no AEs of a given type occur in the study, we can be 97% confident that they will occur in fewer than 20% of people once RD19 is implemented. Also with 25 subjects, the chance of observing at least one AE of probability 5% or more is 90%. Therefore, if no AEs of a given type occur in the study, we can be 90% confident that such adverse event will occur in fewer than 5% of people once RD19 is implemented.

| N | “True” Event Rate | Probability of Observation (%) |
|---|-------------------|--------------------------------|
| 2 | 0.1% | 2.5 |
| | 0.5% | 12.0 |
| | 1.0% | 23.4 |
| | 2.0% | 43.4 |
| | 3.0% | 61.3 |
| | 4.0% | 74.8 |
| | 5.0% | 90.3 |
| | 10.0% | 92.4 |
| | 15.0% | 94.3 |
| | 20.0% | 97.5 |

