4. STUDY POPULATION

Twenty-five (25) males and non-pregnant females, 18 to 45 years of age inclusive, who are in good health and meet all eligibility criteria will be enrolled. The target population should reflect the community at large. The estimated time from initiation of enrollment to completion of the day 1 visit for the last subject enrolled is one week.

Subject Inclusion and Exclusion Criteria must be confirmed by a study clinician, licensed to make medical diagnoses and signatory to The Statement of Compliance as the site PI. Exemptions will be only be granted on Subject Inclusion or Exclusion in rare instances and based on the approval of the Sponsor's Chief Medical Officer.

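### Section 7.2 overstates what 25 subjects can show: the chance of seeing a 5% adverse event is 72%, not 90%, and zero events do not place the rate below 5% with 90% confidence

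*Combined protocol and SAP*

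**What the plan says.** Section 4 sets the size of the trial at 25 subjects. Section 7.1 says that the study "is not designed to test any statistical hypotheses", so there is no power calculation. In its place, Section 7.2 says that "the probabilities of observing one or more AEs given various true event rates are presented in the table below", and it proceeds "With the assumption that all enrolled subjects will likely complete the trial and safety visits in this relatively short duration study".

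Two detection probabilities are then stated in prose, and each becomes a conclusion for the case of no observed events:

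- At a 20% rate: "With 25 subjects, the chance of observing at least one AE of probability 20% or more is approximately 97" per cent, and so "we can be 97% confident that they will occur in fewer than 20% of people once RD19 is implemented".
- At a 5% rate: "Also with 25 subjects, the chance of observing at least one AE of probability 5% or more is 90" per cent, and so "we can be 90% confident that such adverse event will occur in fewer than 5% of people once RD19 is implemented".

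The table beneath gives 97.5% for the 20% row and 90.3% for the 5% row, with eight further rows. Section 7.4.1 plans exact 95% confidence intervals for adverse events in aggregate and by MedDRA category.

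**The concern.** The quantity in Section 7.2 has a simple closed form, and the stated 90% at a 5% rate is far from what that form gives for 25 subjects. The column also rises unevenly: it climbs 15.5 points between the 4% and 5% rows (74.8 to 90.3), then only 2.1 points between 5% and 10% (90.3 to 92.4). A correct column for a fixed sample size would not do that.

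Safety is the primary objective and no hypothesis is tested, so these are the only figures telling a reader what 25 subjects can and cannot show. The text goes beyond detection probabilities and says what may be concluded about future users if an event type is not seen. If that sentence is relied on, a trial with no events of some type would be taken to exclude a rate of 5% or more with 90% confidence, which 25 subjects cannot do. The error runs towards overstated safety for a first-in-man device, and Section 5.1.1 says these safety data will help to settle the regulatory pathway.

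**Working it through.** **Inputs.** n = 25 (Sections 4 and 7.2); all subjects evaluable (the completion assumption in Section 7.2); target quantity P(at least one event) at true rate p (Section 7.2); stated values from the Section 7.2 table and prose. The N column of the table reads 2 in the extracted text. This is probably a truncated 25 and is not counted as an error.

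**Formulas.** P(at least one event) = 1 − (1 − p)^25. The sample size implied by a stated probability P is ln(1 − P) / ln(1 − p).

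| True rate | Stated (%) | Correct, n = 25 (%) | Stated minus correct (points) | Implied n |
|---|---|---|---|---|
| 0.1% | 2.5 | 2.5 | 0.0 | 25.3 |
| 0.5% | 12.0 | 11.8 | +0.2 | 25.5 |
| 1% | 23.4 | 22.2 | +1.2 | 26.5 |
| 2% | 43.4 | 39.7 | +3.7 | 28.2 |
| 3% | 61.3 | 53.3 | +8.0 | 31.2 |
| 4% | 74.8 | 64.0 | +10.8 | 33.8 |
| 5% | 90.3 | 72.3 | +18.0 | 45.5 |
| 10% | 92.4 | 92.8 | −0.4 | 24.5 |
| 15% | 94.3 | 98.3 | −4.0 | 17.6 |
| 20% | 97.5 | 99.6 | −2.1 | 16.5 |

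Four rows (0.1%, 0.5%, 1% and 10%) agree within 2 points and six do not. The implied n runs from 16.5 to 45.5, so the column does not come from any one sample size.

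**Attempts to reproduce 90% at a 5% rate.**

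- n = 27 (all devices supplied, Section 5.3.1): 75.0%.
- n = 30: 78.5%.
- n = 50: 92.3%, but the same n gives 63.6% at a 2% rate against 43.4% stated.
- n = 2, as printed: 9.8%.
- Poisson form, 1 − exp(−25 × 0.05): 71.4%.
- At least two events in 25: 35.8%. This variant gives 97.3% at a 20% rate, close to the stated 97%, but the text says at least one, and it fails at 5%.

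None of these explains the table.

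**Missed events at a 5% rate.** 0.95^25 = 27.7%, against 100 − 90.3 = 9.7% implied by the table: 27.7 / 9.7 = 2.9 times as high.

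**What 0/25 supports.** The one-sided upper bound at confidence c is 1 − (1 − c)^(1/25):

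- 90%: 1 − 0.10^(1/25) = 8.8%
- 95%: 1 − 0.05^(1/25) = 11.3%
- Two-sided exact 95%: 1 − 0.025^(1/25) = 13.7%

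Confidence that the rate is below 5% is 1 − 0.95^25 = 72.3%. Confidence that it is below 20% is 1 − 0.80^25 = 99.6%.

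**Size needed for the stated claim.** ln(0.10) / ln(0.95) = 44.9, so 45 subjects.

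**The case against.** The arithmetic at 5% cannot be defended, and a broken table does not explain it, because the prose repeats the figure. The case on the other side concerns scope and consequence.

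- *Not every figure is wrong.* Four of the ten rows are close to correct. The 20% statement gives the wrong probability but is cautious, and its conclusion of a rate below 20% stands. This is right: only the 5% statement gives false reassurance.
- *Nothing in the design depends on these figures.* No target probability was used to choose 25, the pausing rules in Section 5.5.1 use event counts, and Section 7.2 itself warns that rare events are beyond a study of this size. This also stands, and is why the sample size can stay. The warning does not cure a specific false claim about a 5% rate.
- *The results would be reported under Section 7.4.1, whose exact intervals will be correct.* It is indeed not certain that the Section 7.2 sentences would be carried into the report, and Section 7.4.1 states a method, not a bound. But the Section 7.2 sentence is written as the conclusion to draw when no event occurs. For 0/25 the planned exact interval would reach 13.7%, beside a protocol claim of under 5%. The confidence levels differ, but at a matching one-sided 90% the bound is still 8.8%.
- *The bounds need 25 evaluable subjects.* Section 5.5.3 does not replace subjects lost after device use, and the per-protocol sets may be smaller. If 23 were evaluable (an assumption for illustration), the one-sided 95% bound would be 1 − 0.05^(1/23) = 12.2%. The corrected text should carry that condition.

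**Conclusion.** The concern holds. At a true rate of 5% the detection probability is overstated by 18 points (90.3% against 72.3%), and the claim of 90% confidence in a rate below 5% is false: the confidence is 72%. The rows from 2% to 5% are too high and the 15% and 20% rows too low. The result rests on independent subjects with a common event rate and on all 25 being evaluable, as Section 7.2 assumes; fewer evaluable subjects would weaken the 5% claim further. The correction is required because the error overstates safety on the primary objective. It does not affect the conduct of the trial or the planned analysis.

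**What to change.** Keep 25 subjects. In Section 7.2:

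1. Show N = 25 in the table and replace the probability column, from 0.1% to 20%, with 2.5, 11.8, 22.2, 39.7, 53.3, 64.0, 72.3, 92.8, 98.3 and 99.6, giving the formula 1 − (1 − p)^25.
2. Replace the two pairs of sentences on the 20% and 5% rates with:

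> With 25 evaluable subjects, the probability of at least one AE of a given type is 72% if its true rate is 5%, 93% if it is 10% and 99.6% if it is 20%. If no AE of that type is observed in 25 evaluable subjects, the one-sided 95% upper confidence bound on its rate is 11.3% (90% bound: 8.8%).

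3. Add that a two-sided exact 95% interval for 0/25, the type planned in Section 7.4.1, has an upper limit of 13.7%, so that the two sections agree.

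The cost is a wording change in one section and a less favourable statement at the 5% rate. No subjects, visits or analyses are added. If the sponsor wants to keep 90% detection at a 5% rate, that would take 45 evaluable subjects.

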7.3 Populations for Analyses

The full safety analyses population is by intention-to-treat (ITT) including all subjects who received at least a single use of RD19.

A modified per protocol population for analyses will include all study volunteers who complied with study procedures and remained on study, per protocol, until at least the day 7 clinic visit.

The per protocol population for analyses will include all study volunteers who complied with all protocol procedures and remained on the study until their day 14 visit.

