This first-in-man (FIM) phase I study will evaluate the acute safety, tolerability, device acceptability for use among 25 healthy volunteers between the age of 18 and 45. Based on the results of extensive in-house research, a single dose (9 Joules/cm²) and schedule (twice a day for 3 minutes, separated by at least 4 hours, ideally 8 to 12 hours apart) will be evaluated.

Safety and tolerability (local reactogenicity) will be assessed actively at study day screening (baseline set), 1, 7 and 14, and on non-clinic visit days by collection of these data by history during clinic visits via a memory aid (diary cards). Volunteers will be encouraged to contact designated clinical trial staff for AEs of a medically-urgent nature as soon as is practically possible and to seek immediate medical care, if needed.

Metabolic, liver and kidney safety laboratory evaluations, as well as urinalysis, will be performed at screening and at Day 14 or early termination (and potentially during unscheduled) clinic visits. Hematological safety assessments will be performed at all visits.

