1.1.2 Objectives and Endpoints

Table 1: Objectives and Endpoints (Outcome Measures)

| OBJECTIVES | ENDPOINTS (OUTCOME MEASURES) |
|------------|--|
| Primary | 
Evaluation of the safety and reactogenicity of the RD19 device. 
Frequency, grade and attribution of each incident local and systemic AE during the 14 day study period.Frequency and attribution of any incident SAEs during the 14 day study period. |
| Secondary | 
Evaluation of the acceptability of the EmitBio™ RD19 device. 
Ease of use, clarity of user instructions, & compliance with per protocol schedule and, if out of compliance, reason(s) for non-compliance. |

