1.1.4 Study Key Characteristics

Study Phase

- I

Study Population

- Twenty-five (25) males and non-pregnant females, 18 to 45 years of age, inclusive, who are in good health and meet all eligibility criteria will be enrolled.

Sites

- Carolina Phase I, Raleigh, NC

RD19 Device

- The EmitBio™ RD19 device emits visible blue light to stimulate host defenses (as explained below) and eliminate invading pathogens in the oropharynx and surrounding tissues. The RD19 device does this without additional photosensitizers or chemical reagents that are typically employed with traditional photodynamic therapies. Specifically, selected wavelengths of light have been evaluated across the visible spectrum, and it was discovered that a narrow wavelength band blue light emitted from non-coherent LED sources could perform both of the following functions: upregulate the sustained production of nitric oxide in epithelial tissue through the increase of NO synthases (NOSs); and stimulate the instantaneous release of the body's bound stores of nitric oxide. Nitric oxide also induces and recruits effector cells of the innate immune system, including natural killer (NK) cells, neutrophils and macrophages to phagocytize virus-infected cells at the site of primary infection.

Table 2: Treatment Group

| Group | RD19 | Duration |
|-------|------|------------|
| OL | 25 | 3' x 2/day |

Study Duration

- The duration of the entire study is anticipated to be \leq 18 days (from start of screening to last subject last visit).

Subject Duration

- The duration on trial for each individual subject is \leq 18 days (from start of screening to last visit).

Safety

- The study will use study pausing rules
- This study will involve the Sponsor's Chief Medical Officer as medical monitor, who along with the study PI(s) will assess severe AEs and SAEs, and together will constitute the attribution team.

1.2 Schedule of Activities (SOA) - Table 3

| Study Procedures | Screening Visit | Preliminary Observation | Full Assessment Period | |
|------------------------------------|-----------------|---|---|---|
| Study Day | ≤ -7 to 0 | 1 | 7 | Day 14/ Early Term |
| Study Procedures | | | | |
| Informed Consent | X | | | |
| Inclusion/Exclusion Criteria | X | X | | |
| Demographics Questionnaire | X | | | |
| Medical History | X | * Changes since last visit only | *Changes since last visit only | *Changes since last visit only |

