2.1.1 EmitBio™ RD19 Device Characteristics:

| Characteristic | Target |
|--------------------------------------|--|
| Route of Administration | Oral Illumination |
| Device Configuration | Hand-held, rechargeable |
| Blue Light Source | Non-coherent, light emitting diode (LED) array |
| UVA Content (315 nm – 400 nm) | <1% |
| UVB Content (280 nm - 315 nm) | not detectable* |
| UVC Content (100 nm - 280 nm) | not detectable* |
| Target Exposure Area | Oropharynx and surrounding tissues |
| Exposure Time | 3 min per treatment, 2X/day at least 4 hrs apart |
| Single Light Dose (@ 90 mm) | ~ 9 J/cm ² Joules = Watts x seconds |
| Total Daily Dose (@ 90 mm) | ~ 18 J/cm ² |
| Depth of Tissue Penetration | < 0.5 mm |
| Temperature (IEC 60601-1) | < 48 °C (for durations <10 min) |

*UVA/UVB not detectable in Labsphere 1M Integrating Sphere equipped with CDS-610 Mini CCD Array Spectrometer

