7.4.2 Analysis of the Secondary Endpoint(s)

Summaries and analysis of acceptability variables will be presented for both the modified and per-protocol study populations.

Device use and protocol procedures compliance rates will be calculated and presented.

A device acceptability source document has been created and provided to DCAC for database build and e-CRF production. Descriptive statistics for each variable will be calculated and presented.

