8.1.8 Protocol Deviations

A protocol deviation is any non-compliance with the clinical trial protocol, any process that is noted in the protocol and refers to details in the protocol or GCP requirements, or any critical study procedures with specific instructions in ancillary documents referenced in the protocol.

The non-compliance may be either on the part of the subject, the participating clinical site PI, or the study site staff. Following a deviation(s), corrective actions should be developed by the site and implemented promptly. All individual protocol deviations will be addressed in study volunteer study records.

It is the responsibility of the participating clinical site PI and study staff to use continuous vigilance to identify and report deviations within five working days of identification of the protocol deviation, or within five working days of the scheduled protocol-required activity. All deviations must be promptly reported to EmitBio Inc's Senior Clinical Program Manager. Protocol deviations must be sent to the IRB of record. The participating clinical site PI and study staff are responsible for knowing and adhering to the IRB requirements. A completed copy of an approved Protocol Deviation Form must be maintained in the Regulatory File, as well as in the subject's chart if the deviation is subject specific.

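### The per-protocol and modified per-protocol sets have no compliance tolerance, list of excluding deviations or visit windows, yet the per-symptom confidence intervals and all acceptability summaries are placed on them

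*Combined protocol and SAP*

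**What the plan says.** All references are to the combined protocol and SAP.

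- **Sets.** Section 7.3 defines three. The safety population is everyone with at least one use of the device. The modified per-protocol set is volunteers who "complied with study procedures and remained on study, per protocol, until at least the day 7 clinic visit". The per-protocol set is "all study volunteers who complied with all protocol procedures and remained on the study until their day 14 visit".
- **What has to be complied with.** The synopsis (section 1.1) sets device use at "twice a day for 3 minutes, separated by at least 4 hours, ideally 8 to 12 hours apart", and section 2.1.1 repeats it as "3 min per treatment, 2X/day at least 4 hrs apart". Section 6.2 adds a diary card for every study day and a survey after device use in the clinic. The schedule of activities (Table 3) lists device illumination among the study procedures. It shows Days 7 and 14 as single days; only screening has a range.
- **Deviations.** Section 8.1.8 says "A protocol deviation is any non-compliance with the clinical trial protocol" and makes no distinction between major and minor. Its five working days are a limit for reporting a deviation, not a visit window.
- **Where the sets are used.** Section 7.4.1 opens by placing safety summaries on the safety population. It then adds an analysis of each solicited symptom, reduced to present or absent, with exact confidence intervals, grouped by one or other per-protocol set. Section 7.4.2 states: "Summaries and analysis of acceptability variables will be presented for both the modified and per-protocol study populations".
- **Endpoint.** Sections 1.1.2 and 3.2 include compliance with the schedule, and the reasons for non-compliance, in the secondary endpoint.

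**The concern.** Taken at its word, the per-protocol rule is all or none: one lapse in a two-week schedule of twice-daily home use and daily diary entries takes a subject out. The modified rule leaves out the word *all* but gives no threshold either. Two analysts could therefore build different sets from the same data.

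Two things are at stake. The first is precision: the per-symptom intervals and acceptability results would come from fewer than 25 subjects, by an amount the plan does not anticipate. The second is selection. A subject who skipped uses because of discomfort or dislike of the device is informative about both symptoms and acceptability, and is the kind of subject these sets remove. If the rule is settled only once it proves too strict, an open-label study would be choosing its analysis set with outcomes known.

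**Working it through.** **The plan's own figure.** The plan states no expected size for either set and no adherence rate. Its only precision figures, in section 7.2, assume all 25 subjects. Section 7.2 gives a 90% chance of seeing at least one event at a 5% true rate; the formula gives 1 − 0.95^25 = 72.3%. That is a separate error and nothing below depends on it.

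**Inputs.**
- Subjects: 25 (section 1.1.4).
- Uses: 2 per day (section 1.1) × 14 days (section 1.1.2) = 28 for the per-protocol set. This is derived, not stated; it is 27 if the second Day 14 use is not done. For the modified set, 2 × 7 = 14.
- Adherence per use, *a*: not in the documents, so assumed over a range.
- Confidence level: not stated for the solicited symptoms; 95% assumed, as section 7.4.1 states for other adverse events.

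**Expected set size with independent misses:** 25 × a^m for m uses. For example, 0.95^28 = 0.2378, and 25 × 0.2378 = 5.9.

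**Expected set size with misses clustered within subjects:** beta-binomial with mean *a* and within-subject correlation ρ from 0.05 to 0.20. Put A = a(1−ρ)/ρ and B = (1−a)(1−ρ)/ρ. The chance of no miss is the product over i = 0 to 27 of (A+i)/(A+B+i). At a = 0.95 and ρ = 0.05, A = 18.05, B = 0.95, the chance is 0.410, and 25 × 0.410 = 10.3.

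| Assumed adherence per use | Per-protocol, 28 uses, independent | Per-protocol, 28 uses, clustered | Modified, 14 uses, independent |
|---|---|---|---|
| 99% | 18.9 | not run | 21.7 |
| 98% | 14.2 | 17.6–21.0 | 18.8 |
| 95% | 5.9 | 10.3–16.0 | 12.2 |
| 90% | 1.3 | 4.1–10.2 | 5.7 |

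Using 27 uses changes little (6.3 instead of 5.9 at 95%). At 95% with independent misses, the central 90% range for the per-protocol set is 3 to 10 subjects. Only missed uses are counted; diary lapses, short intervals between uses and shifted visits would lower the figures further under the same literal reading.

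**Effect on the intervals.** With no events in n subjects the exact 95% upper limit is 1 − 0.025^(1/n):
- n = 25: 13.7%
- n = 19: 17.6%
- n = 16: 20.6%
- n = 14: 23.2%
- n = 12: 26.5%
- n = 10: 30.8%
- n = 6: 45.9%

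**With a tolerance.** At an illustrative 80% of uses (0.8 × 28 = 22.4, so at least 23 of 28) and independent misses, the expected per-protocol size is 24.9 at 95% adherence and 23.6 at 90%.

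**The case against.** Much of the case on the other side stands.

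- **Primary safety.** A reader might infer that the safety conclusions rest on the per-protocol set. They do not. Solicited events by maximum severity, unsolicited and serious events, laboratory data, and the exact intervals in aggregate and by MedDRA category fall under the opening sentence of section 7.4.1 and use everyone treated. The study is descriptive (section 7.1), so no decision rule depends on set size. The wording about grouping by per-protocol set is also loose, and may be meant to mirror the Day 7 and Day 14 periods.
- **One missed use excludes.** This is the literal reading, not a stated rule. Section 7.4.2 names device use and protocol procedures separately, so *all protocol procedures* may not cover every home use. Section 7.3 does not cite section 8.1.8. If any lapse excluded a subject, compliance in the per-protocol set would be complete by construction, which suggests that zero tolerance was not intended. This weakens the claim of a strict rule but confirms that membership is undefined.
- **Near-empty sets.** A reader might infer that only a few subjects would remain. With independent misses that needs adherence of about 95% or lower; at 98% or 99% the per-protocol set keeps about 14 or 19. Misses usually cluster within people, and reminders (section 4.3.2) and payment tied to completing procedures (section 4.3.3) favour adherence. The modified set carries the same results and is expected to be larger.
- **Visit days.** A reader might infer that a visit one day early or late is disqualifying, and that some start days force weekend visits. The documents do not say that a nominal day is exact, do not fix start days, and do not say the unit is closed on any day. What remains is that no window is stated.

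None of this supplies the missing tolerance or moves the two analyses onto the all-treated population.

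**Conclusion.** The point holds for both compliance-based sets. Their membership cannot be settled from section 7.3, and following the plan puts the per-symptom intervals and the acceptability results on selected subjects, fewer than 25 unless compliance is complete. Under the literal reading, the upper limit for a symptom never seen would rise from 13.7% with all 25 subjects to about 18% at 99% adherence and 23% at 98%. At 95% it would be about 21% to 31% with clustered misses and 46% with independent ones. These sizes rest on assumed adherence, a derived count of about 28 uses, and every home use counting as a procedure. The selection problem needs none of those assumptions: acceptability, of which compliance is a part, is summarised only among those judged compliant. It should be corrected before data review, but it does not undermine the main safety summaries.

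**What to change.** Before data review:

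1. Restate both sets in section 7.3 with a fixed tolerance, for example at least 80% of scheduled uses to Day 7 (modified) or Day 14 (per-protocol), and no deviation from a pre-listed set that affects the safety evaluation. The 80% is illustrative, since the documents offer no figure. What matters is that one is fixed in advance. Say whether home use counts as a protocol procedure.
2. State an analysis window for the Day 7 and Day 14 visits in section 7.3 and Table 3.
3. In sections 7.4.1 and 7.4.2, report the per-symptom proportions with exact intervals and the acceptability variables on the all-treated safety set, with the two per-protocol sets as supportive. Name the population for the compliance rates, which section 7.4.2 leaves open.

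The cost is wording and one more set of tables, with no added subjects and no change to device use. The downside is that the per-protocol sets will include subjects with minor lapses; these can be listed. The third change matters most, because a looser per-protocol set on its own would still select on compliance.
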